6.4.1.2. Patient's Global Assessments of Disease Activity

The Patient's (Subject's) Global Assessments of Disease Activity (Appendix E) is an assessment of how active a subject's psoriatic arthritis was on average during the last week. The subject will be asked to place a vertical line on a visual analogue scale (VAS) on which the left-hand boundary represents the lowest level of disease activity and the right-hand boundary represents the highest. Distance from the mark to the left-hand boundary will be recorded in millimeters, except when calculating cDAPSA score, where the distance will be calculated in centimeters.

6.4.1.3. Patient's Pain Visual Analogue Scale

The pain visual analogue scale (VAS) is the subject's assessment of how much pain he/she had, on average, last week in his/her joints due to PsA. The subject will be asked to place a vertical line on a VAS on which the left-hand boundary represents "no pain," and the right-hand boundary represents "pain as severe as can be imagined" (Appendix E). The distance from the

mark to the left-hand boundary will be recorded in millimeters, except when calculating cDAPSA score, where the distance will be calculated in centimeters.

6.4.1.4. HAQ-DI

The HAQ-DI (Appendix F; Fries, 1980) is a 20-question, self-administered instrument that measures the subject's functional ability on a 4-level difficulty scale (0 to 3, with 0 representing normal or no difficulty; and 3 representing an inability to perform). Eight categories of functioning are included: dressing, rising, eating, walking, hygiene, reach, grip, and usual activities (Bruce, 2003). This scale is sensitive to change and is a good predictor of future disability (Aletaha, 2006).

6.4.1.5. Enthesitis: Leeds Enthesitis Index

In the evaluation of MDA-Joints, enthesitis will be assessed by the Leeds Enthesitis Index (LEI) (Appendix G; Healy, 2008).

For the LEI, pain will be assessed at the following entheses (tendon insertions): Lateral epicondyle humerus (left/right (L/R)); Medial condyle femur (L/R); Achilles tendon insertion into calcaneum (L/R). The LEI ranges from 0 to 6.

6.4.1.6. BSA

[figure not shown]
BSA (Appendix H) is a measurement of involved skin. The overall BSA affected by psoriasis is estimated based on the palm area of the subject's hand (entire palmar surface or "handprint"), which equates to approximately 1% of total body surface area. All subjects will have their BSA assessed by the Evaluator.

6.4.1.7. Physician's Global Assessments of Disease Activity

The Physician's (Evaluator's) Global Assessments of Disease Activity is an assessment of how active a subject's psoriatic arthritis was on average during the last week. For the Physician's (Evaluator's) Global Assessments of Disease Activity, evaluator should mark a single vertical mark on a 100-mm VAS (see Appendix E), with zero representing the lowest level of disease activity or pain and 100 representing the highest. The distance from the mark to the left-hand boundary of the scale will be recorded in millimeters (Appendix E, Felson, 1995).

6.4.2. Enthesitis: In addition to assessment by the Leeds Enthesitis Index (Section 6.4.1.5), enthesitis will also be assessed using the

6.4.3. Dactylitis

6.4.4. Clinical Disease Activity Index for Psoriatic Arthritis (cDAPSA)

The cDAPSA score (Appendix K) is based on the numerical summation of 4 disease activity variables: tender and swollen joints, patient global and pain assessments on a 10 cm Visual Analogue Scale (VAS) (Appendix E). Proposed cut-offs for cDAPSA are a score \leq 4 for remission, a score > 4 and \leq 13 for low disease activity, > 13 and \leq 27 for moderate disease activity, and > 27 for high disease activity. Evaluation of components of cDAPSA is described above. The calculation of the cDAPSA will be performed programmatically.

6.4.5. Psoriatic Arthritis Disease Activity Score (PASDAS)

The PASDAS (Helliwell, 2014; Appendix L) is a weighted index comprising assessments of joints, function, acute-phase response, quality of life (QOL), and patient and physician by VAS. The calculation of the PASDAS will be performed programmatically using the formula below:

PASDAS = $((0.18 \times \sqrt{Physician global VAS}) + (0.159 \times \sqrt{Patient global VAS}) - (0.253 \times \sqrt{SF36} - PCS) + (0.101 \times LN (Swollen joint count + 1)) + (0.048 \times LN (Tender joint count + 1)) + (0.23 \times LN (Leeds Enthesitis Count + 1)) + (0.377 \times LN (Dactylitis count + 1)) + (0.102 \times LN (CRP + 1)) + 2)*1.5.$

Note: LN = natural logarithm, PCS = physical component summary scale of SF36, CRP = C-reactive protein in mg/l, SF36 = Medical Outcomes Study Short Form-36. All VAS scores are 0–100 mm. Swollen joint count is 66 joints, and tender joint count 68. The score range of the PASDAS is 0–10, with worse disease activity represented by higher scores. Definition of good or moderate response is detailed in Appendix L.

6.4.6. High sensitivity C-reactive Protein

High sensitivity C-reactive protein (hsCRP) and rheumatoid factor will be performed at a central laboratory along with the other clinical laboratory assessments described in Section 6.5.7.

6.5. Safety Assessments

In addition to daily safety monitoring conducted by Investigators and individual study personnel, AEs, serious adverse events (SAEs), discontinuations and laboratory findings will be reviewed by the study team. The review follows the Council for International Organizations for Medical Sciences, Working Group VI (CIOMS VI) recommendations.

The study will be conducted in compliance with the ICH of Technical Requirements for Registration of Pharmaceuticals for Human Use/GCP and applicable regulatory requirements.

The following assessments will be conducted as outlined in Table 13, Table of Events.

6.5.1. Serum and Urine Pregnancy Tests for Females of Childbearing Potential

A serum pregnancy test with a sensitivity of \leq 15 mIU/mL will be required for FCBP subjects at Screening and the Week 48 Visit (or at the Early Termination Visit for subjects who prematurely discontinue from the study). Urine pregnancy test will be performed on all FCBP subjects at the Baseline Visit, prior to randomization. A urine pregnancy test kit will be provided by the central laboratory. Pregnancy tests should be performed if the FCBP subject has missed a menstrual period or the contraception method has changed.

In addition to the assessments specified in Table 13, the Investigator will follow country guidelines regarding the monitoring of pregnancy testing at any scheduled or unscheduled visit and will document the test result in the source document. At the discretion of the Investigator, a serum pregnancy may be done.

6.5.2. Vital Signs, Height and Weight

Vital signs, including temperature, pulse, and seated blood pressure, will be taken during the visits indicated in Table 13, Table of Events. Height will be measured and recorded at Screening; weight will also be measured and recorded at every visit.

In the event of unexplained and clinically significant weight loss, subjects should be evaluated and discontinuation of study treatment should be considered by the Investigator.

6.5.3. Complete/Limited Physical Examination

A complete physical examination includes evaluations of skin, nasal cavities, eyes, ears, lymph nodes, and respiratory, cardiovascular, gastrointestinal, neurological, and musculoskeletal (assessment of joints and spine) systems. A complete physical examination is done at Screening and other designated visits as indicated in Table 13, Table of Events. A limited physical examination includes evaluations of skin, lymph nodes, and respiratory, cardiovascular, and

musculoskeletal systems. A limited physical examination is done at the Baseline Visit and other designated visits as indicated in Table 13.

6.5.4. Psychiatric Evaluation

Treatment with apremilast is associated with an increase in adverse reactions of depression. Before using apremilast in subjects with a history of depression and/or suicidal thoughts or behavior, the Investigator should carefully weigh the risks and benefits of treatment with apremilast in such patients. Subjects should be advised of the need to be alert for the emergence or worsening of depression, suicidal thoughts or other mood changes, and if such changes occur to contact the Investigator.

If a subject suffers from new or worsening psychiatric symptoms, or if suicidal ideation or suicidal attempt is identified, it is recommended to discontinue the subject participation to the study (see Section 11).

6.5.5. Diarrhea, Nausea and Vomiting

Apremilast has been associated with AE reports of diarrhea in clinical trials. Most diarrhea events were of mild or moderate severity and reported within the first 2 weeks of treatment, usually resolving within 4 weeks without medical intervention.

Diarrhea is the passage of three or more loose or liquid stools per day, or more frequently than is normal for the individual (World Health Organization [WHO], 2013). Following the definition of diarrhea by the WHO and taking a more conservative approach, the AE of diarrhea in this protocol is defined as having two or more watery/liquid stools in a day.

To better characterize diarrhea and to distinguish similar events coding to the Medical Dictionary of Regulatory Activities (MedDRA) preferred term of diarrhea, subjects reporting diarrhea or similar events (eg, frequent bowel movements, loose bowels, etc.) will be asked whether they have had two or more watery/liquid stools in a day. Subjects who respond "yes" to this question will be further asked how often, on average, have they experienced two or more watery/liquid stools in a day. Subjects who respond "no" to the question will not be asked any further questions. This data will be reported via electronic data capture in the ERT tablet. If an AE is identified by the Investigator, the AE and respective attributes will be reported in the clinical database. If the AE meets serious criteria, it must be reported to Amgen Global Patient Safety (see Section 10.5).

There have been post-marketing reports of severe diarrhea, nausea, and vomiting associated with the use of apremilast. Most events occurred within the first few weeks of treatment. In some cases, patients were hospitalized.

Subjects 65 years of age or older and subjects taking medications that can lead to volume depletion or hypotension may be at a higher risk of complications. Subjects should be monitored for the occurrence of severe diarrhea, nausea and vomiting. If a subject develops severe diarrhea, nausea and vomiting, discontinuation of study treatment may be necessary (see Section 11).

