With the aim to mitigate potential dose-related side effects associated with apremilast, such as headache and gastrointestinal (GI) disturbances, apremilast-treated subjects will be dose-titrated from 10 mg BID to 20 mg BID to 30 mg BID over the first 5 days of treatment (Table 14). Subjects assigned to placebo will receive 10-, 20-, and 30-mg placebo tablets in blister cards (treatment cards) which are identical in appearance to the corresponding strength apremilast tablets. Apremilast will be provided in blister cards as either 10 mg, 20 mg or 30 mg tablets. The

5-day titration period will also be initiated for the placebo arm after the following visits: the Baseline, Week 16 (early escape), and Week 24. The original treatment assignments (apremilast 30 mg BID or placebo) will remain blinded throughout the study.

At the Week 16 Visit, subjects with no improvement in SJC (sentinel joints) at Week 16 are eligible for early escape, at the discretion of the Investigator and will receive early escape treatment with apremilast 30 mg BID. The joints monitored for early escape must correspond to those affected at the Baseline Visit (sentinel joints). Refer to Section 4.2; Inclusion #6. Subjects will receive the following treatment:

- o Subjects who were randomized to apremilast (30 mg BID) at the Baseline Visit will continue to take apremilast 30 mg BID.
- o Subjects who were randomized to placebo at the Baseline Visit will be switched to receive apremilast (30 mg BID) and will be dose-titrated as described above.

After the Week 24 Visit, subjects will be offered to enter the Active treatment Extension Phase. All subjects enrolled in the Extension Phase will receive treatment with apremilast (30 mg BID) until the end of the study (ie, up to the Week 48 Visit) or until early discontinuation. Placebo subjects will be dose titrated. All subjects will receive treatment cards of identical appearance to maintain the blinding of the original treatment assignments (apremilast 30 mg BID or placebo).

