7.3. Method of Treatment Assignment

After the informed consent is signed, subjects will be assigned a subject identification number using a centralized interactive web response system (IWRS). At the Baseline Visit, a centralized schema will be applied to assign subjects who meet the inclusion and none of the exclusion criteria in a 2:1 ratio to receive either apremilast 30 mg tablets or placebo. The IWRS will stratify the randomized subjects by their use of glucocorticosteroids (yes/no) and use of a csDMARD: (csDMARD-naïve; csDMARD use prior to baseline; or csDMARD use prior to and concomitant at baseline).

Subjects who are randomized to apremilast at baseline will be dose-titrated during their first week of active treatment (see Section 7.2), while subjects who are randomized to placebo will receive identically appearing placebo titration cards while continuing to receive their assigned dose of placebo BID.

Subjects with no improvement in the swollen joint count at Week 16 are eligible for early escape. The joints monitored for early escape must correspond to those affected at baseline (sentinel joints). To maintain the study blind, placebo-treated subjects who escape early will be transitioned in a blinded fashion via an IWRS to apremilast 30 mg BID and apremilast-treated subjects will remain blinded on their original treatment assignment. Placebo subjects will be dose-titrated during their first week of active treatment (see Section 7.2), while subjects who were already on apremilast 30 mg BID will receive identically appearing placebo titration cards while continuing to receive their assigned dose of apremilast 30 mg BID.

At the Week 24 Visit, subjects will be offered to enter a 24-week Active - treatment Extension Phase (Extension Phase). All subjects enrolled in the Extension Phase will receive treatment with apremilast (30 mg BID) until the completion of the study (ie, up to the Week 48 Visit) or until early discontinuation. Placebo subjects will be dose titrated (5-day titration period). All subjects will receive treatment cards of identical appearance to maintain the blinding of the original treatment assignments (apremilast 30 mg BID or placebo).

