#### Appendix A. Analytical Windows

For safety analyses, all available values obtained between 2 planned visits including unscheduled measurements will be pooled to the analysis visit window according to the following definition. In the event of multiple measurements of the same test in the same window, the value measured nearest to the target day will be selected to the window; if they are at the same distance to the target day, the latest one will be used. If the value at a scheduled visit is missing and there is no value available within the time window based on the study day, the value at the study week will be missing.

Table 5. Table for Visit Mapping for by Time Point Analysis

Visit	Target Day	Analysis Time Window for Safety Data
Screening (1)	<1	<1
Baseline (2)	1	1
Week 4 (3)	29	[2, 56]
Week 12 (4)	85	[57, 98]
Week 16 (5)	113	[99, 140]
Week 24 (6)	169	[141, 182]
Week 28 (7)	197	[183, 238]
Week 40 (8)	281	[239, 308]
Week 48 (9)	337	≥309
Target Day = Visit date – Drug start date + 1.		

For Placebo-controlled Phase, target day and relative window are relative to the first dose of IP.

The Apremilast-exposure Period encompasses all apremilast-exposure data, irrespective of when the apremilast exposure starts (at Week 0, 16, or 24). The scheduled study weeks for subjects who are originally randomized to the placebo group and transitioned to apremilast at Week 16/Visit 5 (due to early escape) or Week 24/Visit 6 will be adjusted to reflect the study weeks relative to the transition (i.e., study weeks on apremilast), and mapped to the (unadjusted) scheduled study weeks. Adjusted study weeks on apremilast will align with scheduled study weeks specified in the protocol.

This simple mapping will be ordered first as "minus 16" or "minus 24" from the scheduled visit depending on when the subject started apremilast, and then re-aligned to the

Page 64 of 67

Protocol Number: 20200058
Date: 07 February 2023
Page 65 of 67

protocol scheduled visit. Scheduled weeks are: 0, 4, 12, 16, 24, 28, 40, 48; Placebo subjects who early escaped: 0, 8, 12, 24, 32; placebo subjects who transitioned at week 24: 0, 4, 16, 24. The records related to Week 8 are realigned to Week 4, 32 to Week 28.

Protocol Number: 20200058

## Date: 07 February 2023 Page 66 of 67

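### SAP Appendix A reports early escapers' 8-week laboratory, vital-sign and weight values as Week 4 in the Apremilast-exposure tables

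*Protocol*

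**What the plan says.** A subject can first take apremilast at Week 0 (randomized), Week 16 (placebo, early escape) or Week 24 (placebo, extension). Protocol 7.3 says of the placebo escapers: "Placebo subjects will be dose-titrated during their first week of active treatment".

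Protocol Table 13 has no visit between Week 16 and Week 24. SAP Appendix A lists the same calendar, "Scheduled weeks are: 0, 4, 12, 16, 24, 28, 40, 48", and converts it to weeks on apremilast: "Placebo subjects who early escaped: 0, 8, 12, 24, 32; placebo subjects who transitioned at week 24: 0, 4, 16, 24". It then adds the rule at issue: "The records related to Week 8 are realigned to Week 4, 32 to Week 28".

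Table 5 in the same appendix gives safety windows in days: Week 4 is Days 2 to 56 and Week 12 is Days 57 to 98. The text ties those windows to the first dose of investigational product for the Placebo-controlled Phase. SAP 5.4 makes Appendix A the source of visit labels for safety analyses, and SAP 9.6.1 pools all starters in the Apremilast-exposure Period whenever they began.

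On gastrointestinal events, Protocol 6.5.5 describes most diarrhea as "reported within the first 2 weeks of treatment, usually resolving within 4 weeks without medical intervention", places most severe post-marketing events in the first few weeks, and says: "Subjects should be monitored for the occurrence of severe diarrhea, nausea and vomiting".

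**The concern.** A by-visit table on an exposure clock is read as a time course: the Week 4 row should show subjects about four weeks into treatment. Under the realignment, one identifiable subgroup enters that row after twice that exposure. Laboratory, vital-sign and weight changes that move over the first two months would be averaged across two exposure times under one label, and the reader of the table could not tell. Weight is a monitored safety item in Protocol 6.5.2, so its early course is of some interest.

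The mapping also brings out a feature of the visit calendar. Week 16 starters are the only group with no scheduled visit four weeks after their first apremilast dose, although 6.5.5 places most gastrointestinal events in the first weeks. This is an observation, secondary to the labelling point.

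**Working it through.** **Inputs**
- Visit weeks: 0, 4, 12, 16, 24, 28, 40, 48 (Protocol Table 13; SAP Appendix A).
- Visit windows: ±3 days for Weeks 4 to 28 (Protocol Table 13).
- Target days: Week 4 = 29, Week 12 = 85, Week 16 = 113, Week 24 = 169, Week 28 = 197 (SAP Table 5).
- Assumption: the first apremilast dose falls on the day of the Week 16 or Week 24 visit.

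**Step 1. Reproduce the SAP's weeks on apremilast** (visit week minus start week)
- Start at Week 16: 16, 24, 28, 40, 48 minus 16 = 0, 8, 12, 24, 32. This matches.
- Start at Week 24: 24, 28, 40, 48 minus 24 = 0, 4, 16, 24. This matches.

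**Step 2. On-drug day of the record labelled Week 4** (visit day minus start day plus 1)
- Week 0 starters: Day 29; Days 26 to 32 with ±3 days at one visit.
- Week 24 starters: 197 − 169 + 1 = Day 29; Days 23 to 35 with ±3 days at both visits.
- Week 16 escapers: 169 − 113 + 1 = Day 57; Days 51 to 63 with ±3 days at both visits.

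For visits within window, the two sets of days do not overlap. The latest true 4-week record (Day 35) and the earliest escaper record (Day 51) are 16 days apart.

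**Step 3. Compare with Table 5, if its windows are applied to on-drug days**
- Day 57 lies in Week 12 (57 to 98), not Week 4 (2 to 56). Across the visit window, Days 51 to 56 would be Week 4 and Days 57 to 63 would be Week 12.
- The escapers' true 12-week visit (Day 85) is also in Week 12. Table 5 keeps the value nearest the target day: Day 85 is 0 days away and Day 57 is 28 days away, so the 8-week value would be dropped.
- The companion move, Week 32 to Week 28, fits Table 5: 7 × 32 + 1 = Day 225, inside 183 to 238.

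So the mapping text mislabels the 8-week record, and Table 5 would usually discard it. Neither shows it at its actual exposure time.

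**Step 4. Which outputs are touched**
- Touched: by-time-point summaries and by-visit shifts for laboratory values and vital signs, and by-visit weight summaries, in the Apremilast-exposure Period (SAP 9.6.1, 9.6.4, 9.6.5).
- Not touched: adverse event incidence and exposure-adjusted incidence rates, which count subjects over the period and use event start dates; new events by exposure interval, assigned by start date (SAP 9.6.2); efficacy time points, which use visits as recorded (SAP 5.4).

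**Step 5. Possible size.** The documents give no number of escapers. For illustration only, take one third of 285 = 95 placebo subjects and assume that 20% to 50% escape, a range with no source in the documents. That is 19 to 48 subjects. If all 285 subjects contributed to the pooled Week 4 row, they would be 19/285 = 7% to 48/285 = 17% of it.

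**Step 6. The visit calendar.** The first scheduled visit on apremilast comes at 4 weeks for Week 0 and Week 24 starters and at 8 weeks (56 days) for Week 16 starters. For the last group that is 56 − 14 = 42 days after the 2-week mark and 56 − 28 = 28 days after the 4-week mark in 6.5.5.

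**The case against.** The case for leaving Appendix A alone has weight. The mapping is printed openly, so nothing is hidden. The text wants on-drug weeks aligned with protocol weeks. Week 8 is equally far from Weeks 4 and 12, and escapers already have a Week 12 value, so moving Week 8 to Week 4 keeps a record that would otherwise be lost. Table 5's Week 4 window already runs to Day 56, so that label is coarse by design. Safety analysis is descriptive, and no primary, secondary or adverse event incidence result changes. All of this stands, and it limits the point to a labelling correction. It does not make an 8-week value a 4-week value, and the record can be kept under its own label.

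A reader might infer that Appendix A flatly contradicts Table 5. The documents do not go that far: Table 5 is expressly tied to first dose in the Placebo-controlled Phase, and the Apremilast-exposure Period has its own mapping. What is missing is a statement of which rule governs on-drug days.

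A reader might also infer that early adverse events in escapers go unrecorded for eight weeks. That is not supported. Protocol 6.2 has adverse events evaluated continuously and allows unscheduled visits at the investigator's discretion. Protocol 6.5 refers to daily monitoring by investigators, and 6.5.8 requires recording from consent to 28 days after the last dose, with serious events reported within 24 hours. Scheduled laboratory tests, weight and the visit-based diarrhea questions do wait until Week 24, and the diarrhea answers may then rest on up to eight weeks of recall. Section 6.5.5 sets no monitoring interval, and it describes most diarrhea as mild or moderate. Table 13 also has an 8-week interval, Week 4 to Week 12, for everyone.

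**Conclusion.** The labelling point holds. As written, Appendix A places escapers' 8-week laboratory, vital-sign and weight values in the Week 4 row of the pooled Apremilast-exposure summaries, nominally 28 days later than the other values there (Day 57 against Day 29). This rests only on the visit calendar and the SAP's own arithmetic, with first dose taken on the visit day. How far any Week 4 mean or shift count moves cannot be stated, because neither the number of escapers nor the size of the early changes is in the documents.

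The visit-calendar point is an observation only. It is tempting to read the missing 4-week visit as a contradiction within the protocol, or as half the safety surveillance for this group. The documents support neither: no monitoring interval is set, and counting scheduled visits is not the same as counting event capture. What remains is that 6.5.5 stresses the first weeks of exposure, Table 13 gives one of three starting groups no scheduled visit at four weeks, and the two should be reconciled.

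**What to change.** In SAP Appendix A:
1. Delete the move of Week 8 records to Week 4.
2. Show escapers' 8-week on-drug values in their own Week 8 row and keep them out of the Week 4 row. Make this an explicit exception to the sentence aligning on-drug weeks with protocol weeks.
3. State whether Table 5 or the mapping text governs visit labels on the apremilast clock. If Table 5 is to be used, it needs a Week 8 window, since its Week 4 window ends at Day 56 and its nearest-value rule would favour the Day 85 record in Week 12.

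This takes a short SAP edit and one more row in the by-visit tables. It needs no new data and can be made after all escapers have passed Week 24. The downside is a sparse row, filled mainly by escapers.

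Separately, the sponsor should reconcile Protocol 6.5.5 with Table 13 for subjects who start apremilast at Week 16. How that is done is a clinical matter, and no contact schedule is proposed.
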